1.2 OBJECTIVES

1.2.1 Primary objective

The primary objective of this study is to compare the effect of alirocumab with placebo on the occurrence of cardiovascular events (composite endpoint of coronary heart disease [CHD] death, non-fatal myocardial infarction [MI], fatal and non-fatal ischemic stroke, unstable angina requiring hospitalization) in patients who have experienced an acute coronary syndrome (ACS) event 4 to 52 weeks prior to randomization and are treated with an LMT regimen that is statin-intensive (defined as atorvastatin 40 or 80 mg, or rosuvastatin 20 or 40 mg) or at maximally tolerated dose of these given statins, and optimized for long-term chronic use with other non-statin LMT(s) at Investigator's discretion.

1.2.2 Secondary objectives

The secondary objectives are:

To compare the efficacy of alirocumab versus placebo on secondary endpoints (any CHD event, major CHD event, any cardiovascular [CV] event, composite of all-cause mortality/non-fatal MI/ non-fatal ischemic stroke, all-cause mortality);

- To evaluate the safety and tolerability of alirocumab throughout the study;
- To evaluate the development of anti-alirocumab antibodies;
- To evaluate the effect of alirocumab on low-density lipoprotein cholesterol (LDL-C), apolipoprotein B (Apo B), and non-high-density lipoprotein cholesterol (non-HDL-C).

A Clinical Events Committee (CEC) is established to adjudicate, in a blinded fashion, events corresponding to the primary and secondary cardiovascular endpoints as well as all causes of death.

1.3 DETERMINATION OF SAMPLE SIZE

The sample size calculations are based on the primary efficacy variable, with the following assumptions:

• Primary efficacy endpoint is the time from randomization to the date of first occurrence of one of the following clinical events, as determined by the CEC: CHD death, any non-fatal MI, fatal or non-fatal ischemic stroke, or unstable angina requiring hospitalization (with new high-risk electrocardiogram (ECG) findings and contemporary evidence of angiographically significant coronary disease). Based on PROVE-IT results (1) and considering adjustment based on the study design and endpoints definition, the following Kaplan-Meier probabilities of event in the placebo group have been assumed: 3.8% at 12 months, 6.4% at 24 months, 9.0% at 36 months, and 11.4% at 48 months. Probabilities of an event at other time points are estimated using a piece-wise exponential model. The primary efficacy endpoint will be analyzed on an intent-to-treat basis (all randomized

patients, including those who discontinue study medication are followed for any efficacy event until the CSED).

- Treatment hazard ratio of 0.85 (corresponding to a 15% hazard risk reduction for the test group relative to placebo), which is assumed to be constant over time;
- A log-rank test at an overall 1-sided 2.5% significance level with 90% power;
- Two interim analyses, according to a group sequential design, using for efficacy Gamma (-22) α-spending function, and for futility a Gamma (-5) β-spending function. Non-binding spending functions are used. See Section 4 for interim analysis details;
- One percent lost-to-follow-up prior to a primary efficacy endpoint at 24 months in both arms;
- Enrolment rate: sample size of 18 000 patients enrolled in 1400 sites (all sites were expected to be activated over a 12 months period). Table 1 below describes the expected enrolment rate per month; these assumptions were based on internal experience to enroll this patient population.

Month	1 to 3	4	5	6	7	8	9	10	11	12 to 40
No. patients per month	32	64	80	104	160	240	320	420	520	560
Cumulative no. patients	96	160	240	344	504	744	1064	1484	2004	2564 at M12, 18 000 at M40

Table 1 - Enrolment rate assumptions per month

Based on the above assumptions, 1613 events are needed for 90% power. In order to achieve the 1613 targeted events, 18 000 patients (9000 per group) were initially planned to be randomized, over a period of about 40 months. However taking into account the local situation in China (regulatory requirement to randomize at least 600 patients, and anticipated delay in study start in China), the total number of patients randomized may be increased to approximately 18 600 patients (~9300 per group). At the end of the study, the overall population will include approximately 18 000 randomized patients who have either died or have been followed for a minimum of 24 months, possibly supplemented with an additional subset of Chinese patients (~600) who may be followed for less than 24 months.

Statistical Analysis Plan SAR236553/REGN727-EFC11570 - alirocumab 11-Oct-2017 Version number: 3

2 STUDY PLAN

The following figure presents graphically the study design:

- Final phone/internet follow-up (V31) will be performed 8w after V30

ACS: acute coronary syndrome, LMT: lipid-modifying therapy, MTD: maximal tolerated dose

The study flow chart is detailed in the protocol.

2.1 MODIFICATIONS TO THE STATISTICAL SECTION OF THE PROTOCOL

This section summarizes major changes to the protocol statistical section with emphasis on changes made after study start (after the first patient was enrolled).

The protocol history table below gives the timing, rationale, and key details of major changes to the protocol statistical section.

The first patient was randomized on 02 November 2012.

Amendment Number	Date approved	Rationale	Description of statistical changes
6	05-Dec-2013	Clarification of definition of secondary endpoints in the protocol	The secondary endpoint of "Any hospitalization for unanticipated coronary revascularization procedure" was replaced with "Any ischemia-driven coronary revascularization procedure"
6	05-Dec-2013	Exclusion criteria in the protocol modified to allow inclusion of patients with a qualifying index ACS event occurring more than 16 weeks and less than 52 weeks prior to randomization	"Time from ACS event to randomization" in categorical variable (eg, 4-24 weeks, >24 weeks) is added as a subgroup factor in the Subgroups analyses of the primary efficacy endpoint
6	05-Dec-2013	The endpoint "Cardiovascular events of interest (other than efficacy endpoints)" has been added in the protocol.	The analysis of cardiovascular events of interest (other than efficacy endpoints) is added.
8	16-Apr-2015	Sample size may be increased up to approximately 18 600 patients to allow the inclusion of 600 Chinese patients because of the local delayed study start in China, and definition of the CSED updated	CSED definition modified to "when 1613 patients have experienced at least one primary efficacy event or 24 months after the closing of randomization for all countries except China, whichever comes last"
8	16-Apr-2015	Neurologic events (including neurocognitive events) are added as AESI	Neurologic events (including neurocognitive events) added in the safety analysis

Table 2 - Protocol amendment statistical changes

ACS = acute coronary syndrome; AESI = adverse event of special interest; CSED = common study end date

2.2 STATISTICAL MODIFICATIONS MADE IN THE STATISTICAL ANALYSIS PLAN

The statistical analysis plan history table below gives the timing, rationale, and key details for major changes to the statistical analysis features

- in the first version of the statistical analysis plan dated on 25 January 2016 compared to the protocol amendment 8 (version currently in effect at this time)
- in the amended versions of the statistical analysis plan (versions 2 and 3) compared to the first version of 25 January 2016.

Changes already incorporated in a protocol amendment are listed only in Table 2.

With regard to the study timelines, the first patient was enrolled on 02 November 2012. The first interim analysis occurred in April 2016 with the data cut-off for the interim analysis on 30 November 2015. The second interim analysis occurred when approximately 1210 patients had at least one positively-adjudicated primary efficacy endpoint, with review of the data by the DMC in November 2016.

SAP			
version	Date		
number	approved	Rationale	Description of statistical changes
1	25-Jan-2016	Imputation method not planned for missing lipid values	For patients without lipid values in the time window analyzed, multiple imputation will be used with different imputation strategies depending on the time of those missing values (during the treatment period or after treatment discontinuation) (see Section 3.4.7.4.1)
1	25-Jan-2016	End of analysis period for the analysis of TEAEs for patients with 2 consecutives low LDL-C did not take into account down-titrations from 150 mg to 75 mg	In the specific analysis of TEAEs for the subgroup of patients with two consecutive LDL-C <25 mg/dL (respectively 15 mg/dL) within the alirocumab treatment group, the upper limit of the analysis period for patients down-titrated from 150 mg to 75 mg will end at the date of last injection of 150 mg +70 days (see Section 3.4.5.1).
1	25-Jan-2016	Selection of patients with 2 consecutive LDL-C <25 mg/dL (respectively 15 mg/dL) modified consistently with the other studies of the program.	The patients will be considered as having 2 consecutive LDL-C <25 mg/dL (respectively 15 mg/dL) if these values are spaced out by at least 21 days (see Section 3.1.5.4).
2	28-Jul-2016	Category of patients without diabetes at baseline divided in two sub- categories, consistently with the ODYSSEY Phase 3a program.	The category of patients without diabetes at baseline will be sub-divided in two-sub- categories: "Pre-diabetes" and "normoglyceamic" (see Section 3.1.1). The transition to new onset of diabetes in these two subgroups will be described separately (see Section 3.4.5.3). The primary efficacy endpoint will also be assessed in these subgroups (see Section 3.4.4.1)

Table 3 - Statistical analysis plan statistical changes

Statistical Analysis Plan SAR236553/REGN727-EFC11570 - alirocumab

11-Oct-2017 Version number: 3

SAP			
version	Date		
number	approved	Rationale	Description of statistical changes
2	28-Jul-2016	Per FDA's recommendation, definition of "New onset of diabetes" revised.	The fasting glucose criterion is included in the definition of "New onset of diabetes" (see Section 3.4.5.3). Details about handling of specific data situations are also added.
3	This version	To improve the identification of the diabetes status at baseline and during the course of the study (new onset of diabetes) for patients selected by anti- diabetic medications.	Outcome of the review by external diabetes experts considered in the definition of diabetes status for patients identified with anti-diabetic medications at baseline (see Section 3.1.1) and during the course of the study (see Section 3.4.5.3)
3	This version	Improve derivation of the censoring date for vital status	Additional dates are considered to derive the censoring date for CHD deaths, CV deaths and all causes of deaths endpoints (see Section 3.1.3.2).
3	This version	Include CHD death and CV death endpoints in the hierarchical testing to have a more robust assessment on these efficacy endpoints.	CHD death endpoint is moved from other secondary efficacy endpoints to main secondary efficacy endpoints. In addition CV death endpoint is added in the main secondary endpoints (see Section 3.1.3.2.1).
3	This version	Provide comprehensive assessment of diabetes.	"New onset of diabetes" added in the list of events of interest (see Section 3.1.4.1)
3	This version	Clarification about the list of patients who will have an additional ADA sample after the end of the study.	See Section 3.1.5.5
3	This version	Explore treatment effects on CV events before and after defined timepoints.	Analysis with Cox Proportional hazard models, exploring if the treatment HR varies over time, added in additional analyses on CV events (see Section 3.4.4.4).
3	This version	Avoid overlap between alirocumab period and placebo period for patients switched to placebo with incomplete/missing last active injection date.	Imputation of last active injection if incomplete/missing changed from the day to the day before the first injection of placebo following the switch to placebo in IVRS (see Section 3.5.3)

SAP = statistical analysis plan; TEAE = treatment-emergent adverse event;

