#### 9.1.3 Main Secondary Efficacy Endpoint(s):

- Time from randomization to first occurrence of any CHD event (major CHD event, unstable angina requiring hospitalization, ischemia-driven coronary revascularization procedure)
- Time from randomization to first occurrence of any major CHD event (CHD death, non-fatal MI)

- Time from randomization to first occurrence of any CV event defined as follows: any non-fatal CHD event, any CV death, and non-fatal ischemic stroke
- Time from randomization to first occurrence of all-cause mortality, non-fatal MI, non-fatal ischemic stroke
- Time from randomization to death (all-cause mortality)

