#### **11.4.2.3 Multiplicity consideration**

In order to handle multiple main secondary endpoints, the overall Type-I error will be controlled by the use of a sequential inferential approach. Statistical significance of the primary parameter is

required before drawing inferential conclusions about first key secondary parameter (at the 0.0001 one-sided alpha level at the second interim analysis or at the 0.0249 one-sided alpha level at the final analysis). The order of tests is detailed in [Section 9.1.3](#). Inferential conclusions about successive main secondary parameters require statistical significance of the prior one.

This fixed hierarchical approach will ensure a strong control of the overall type-I error rate at the required one-sided level (0.0001 for the second interim analysis and 0.0249 at the final analysis).

No further adjustments will be made for other secondary endpoints or subgroup analyses for which p-values will be provided for descriptive purpose only.

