3.1.3.2.1 Main secondary endpoint(s)

- Time from randomization to first occurrence of any CHD event (major CHD event, unstable angina requiring hospitalization, ischemia-driven coronary revascularization procedure);
- Time from randomization to first occurrence of any major CHD event (CHD death, nonfatal MI);
- Time from randomization to first occurrence of any CV event (any non-fatal CHD event, any CV death, and non-fatal ischemic stroke);
- Time from randomization to first occurrence of all-cause mortality, non-fatal MI, non-fatal ischemic stroke;
- Time from randomization to CHD death;
- Time from randomization to CV death;
- Time from randomization to death (all-cause mortality).

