3.4.4.3 Multiplicity issues

In order to handle multiple main secondary endpoints, the overall type-I error will be controlled by the use of a sequential inferential approach. Statistical significance of the primary endpoint is required before drawing inferential conclusions about first main secondary endpoint (at the 0.0001 1-sided alpha level at the second interim analysis or at the 0.0249 1-sided alpha level at the final analysis). Inferential conclusions about successive main secondary parameters require statistical significance of the prior one. The order of tests is detailed in Section 3.1.3.2.1.

This fixed hierarchical approach will ensure a strong control of the overall type-I error rate at the required 1-sided level (0.0001 for the second interim analysis and 0.0249 at the final analysis).

No further adjustments will be made for other secondary endpoints for which p-values will be provided for descriptive purpose only.

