4 INTERIM ANALYSIS

Two interim analyses (IA) are planned, when 50% and 75% of the total number of expected events have occurred:

- Interim analysis for futility will be conducted, when approximately 807 events (50% of the targeted number of primary endpoint events) have occurred;
- Interim analysis for futility and overwhelming efficacy will be conducted, when approximately 1210 events (75% of the targeted number of primary endpoint events) have occurred.

Both IAs will be performed by the external independent CV DMC Statistician and will be reviewed under the supervision of the CV DMC. The CV DMC will also review secondary efficacy endpoints and safety data (adverse events, laboratory data, vital signs) available at the time of the IA.

Control of the type I and type II error will be ensured using gamma (-5) spending function for type II error (futility) and Gamma (-22) for type I error (efficacy) at each IA (the type I error spending function is also applied at the first IA, even if the objective of this first IA is only futility). It has to be noted that, in order to protect the global type I error in case the decision is taken to overrule the futility rule, non-binding boundaries were used.

The following table shows the stopping rules at each interim analysis (using the sample size assumptions described in Section 1.3):

Timing of analyses	Stopping boundaries (1-sided p-value and hazard ratio)	
	Futility	Overwhelming efficacy
First IA: 50% of targeted events	p >0.548 (⇔ HR >1.008)	NA
Second IA: 75% of targeted events	p >0.19 (⇔ HR >0.951)	p <0.0001 ^a (⇔ HR <0.802)

Table 10 - Interim analyses stopping boundaries corresponding to Gamma (-22) type I error and
Gamma (-5) type II error spending functions

HR = hazard ratio; IA = interim analysis; NA = not applicable

a Should the second interim analysis be triggered just before or after 1210 events have been reached, the exact nominal significance level to be used at the second IA would be re-computed based on a Gamma(-22) spending function.

Calculations done using EAST® 5.4

The CV data monitoring committee (DMC) could consider early stopping of the study for overwhelming efficacy at the second IA, if the following conditions are met:

- Stopping boundaries for overwhelming efficacy are crossed;
- Positive trend observed for secondary efficacy endpoints, including all cause mortality, and no excess of non-CV mortality;

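### Does SAP version 3 leave it unclear that all-cause mortality is now tested after CHD death and CV death?

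*SAP*

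**What the plan says.** Protocol 9.1.3 lists five main secondary endpoints, ending with "Time from randomization to death (all-cause mortality"), and protocol 11.4.2.3 makes that list the test order. Protocol 9.1.4 places CHD death among the other secondary endpoints. For those, 11.4.2.3 says: "No further adjustments will be made for other secondary endpoints or subgroup analyses for which p-values will be provided for descriptive purpose only". CV death on its own is in neither protocol list.

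The version 3 row of SAP 2.2, Table 3 records that "CHD death endpoint is moved from other secondary efficacy endpoints to main secondary efficacy endpoints" and that CV death is added. It then refers the reader to 3.1.3.2.1. The stated rationale is "Include CHD death and CV death endpoints in the hierarchical testing to have a more robust assessment on these efficacy endpoints".

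SAP 3.1.3.2.1 lists seven endpoints. The fifth is "Time from randomization to CHD death", the sixth is CV death and the last is all-cause mortality. SAP 3.4.4.3 names that list as the order of tests and sets the gate: "Inferential conclusions about successive main secondary parameters require statistical significance of the prior one". SAP 1.2.2 still describes the secondary objectives by the five earlier endpoints, ending in "non-fatal ischemic stroke, all-cause mortality".

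**The concern.** In a fixed sequence, an endpoint's position decides what can be claimed for it. Table 3 is introduced as giving the rationale and key details of major changes, yet the row is silent on position and does not mention that two gates now stand ahead of all-cause mortality. A reader of the protocol, the SAP objectives or the log row alone would not learn this. That reader would also find CHD death descriptive in the protocol and confirmatory in the SAP.

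Three things seem to raise the stakes:

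- All-cause mortality is the only secondary endpoint named in the conditions for stopping early for efficacy: "Positive trend observed for secondary efficacy endpoints, including all cause mortality, and no excess of non-CV mortality".
- Version 3 is dated 11 October 2017, after the data monitoring committee reviewed the second interim analysis in November 2016.
- The SAP sentence on descriptive p-values covers only the other secondary endpoints. It does not mention a main endpoint that sits below a failed gate.

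The fear is a later dispute over which list governs the mortality claim.

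**Working it through.** **1. Which list governs?**

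| Place | Endpoints listed | Rank of all-cause mortality | Sets the test order? |
|---|---|---|---|
| Protocol 9.1.3 with 11.4.2.3 (25 Feb 2016) | 5 | 5th | Yes, at that date |
| SAP 1.2.2 (version 3) | 5 | none stated | No, it states objectives |
| SAP 2.2, Table 3, version 3 row | logs two additions | none stated | No, refers to 3.1.3.2.1 |
| SAP 3.1.3.2.1 with 3.4.4.3 (11 Oct 2017) | 7 | 7th | Yes |

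Only one place in the SAP sets an order. The log row names the old status of CHD death, its new status and the section to consult. The protocol list is therefore the state before a recorded change and not a competing rule.

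**2. Is the consequence stated?** The gate in 3.4.4.3, applied to the list in 3.1.3.2.1, gives it directly: no inferential conclusion on mortality unless CHD death and CV death are both significant. SAP 3.4.4.2 applies the primary-endpoint methods to the secondary endpoints, that is, the stratified log-rank test and the Cox hazard ratio with its interval (3.4.4.1). Mortality is thus estimated and reported whatever happens above it.

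**3. Type I error.** The plan's own figure first: 4(1.960 + 1.2816)² / (ln 0.85)² = 1592 events, and 1613 once the two interim analyses and their spending functions are included, which matches the plan. The final one-sided level carried down the hierarchy is 0.0249 (critical value 1.962). A fixed sequence set before unblinding holds that level in any order. With the earlier steps passed and no effect on any death category, the simulated error is 0.025 whether mortality or CHD death comes first.

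**4. What the order does to a mortality claim.** The documents give no death counts, so CHD / CV / all deaths are assumed to run from 300/370/550 to 450/550/800. Log-rank scores for CHD, other CV and non-CV deaths are drawn independently, each with mean −ln(HR)·d/4 and variance d/4, and summed to give nested Z statistics (1,000,000 draws). The protocol order needs Z for all deaths to exceed 1.962. The SAP order needs all three Z statistics to do so. Earlier gates are not conditioned on.

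Check on the protocol order at HR 0.85: Φ(0.1625·√550/2 − 1.962) = 0.478 and Φ(0.1625·√800/2 − 1.962) = 0.632.

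| Effect on deaths | Protocol order | SAP order | Loss |
|---|---|---|---|
| HR 0.85 on all deaths | 0.478 to 0.632 | 0.227 to 0.347 | 0.251 to 0.285 |
| HR 0.85 on CV deaths, 1.0 on non-CV | 0.248 to 0.351 | 0.164 to 0.260 | 0.084 to 0.091 |
| HR 0.75 CHD, 0.80 other CV, 1.0 non-CV | 0.584 to 0.764 | 0.517 to 0.725 | 0.067 to 0.040 |

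Putting mortality ahead of CHD death would cost the CHD-death claim about 0.04, 0.12 to 0.14, and 0.13 to 0.18 in the three rows. The order is a trade-off between claims.

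**5. Would better wording move any of this?** No. Stating the ranks in Table 3, restating the gate, or updating SAP 1.2.2 leaves the order, the alpha and every probability above as they are.

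**The case for a change.** The best case for acting is that position is a key detail under Table 3's own description, and that a late change which lowers the rank of mortality is where a recorded reason is most useful. The cost would be a few sentences. It is also true that SAP 1.2.2 is inconsistent with 3.1.3.2.1 inside one document, and that this cannot be put down to an earlier date.

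These points of fact stand, but they concern the record and not the analysis. SAP 1.2.2 repeats the protocol objectives and sets no order, gate or level. The log row does give a reason for including the two endpoints. A separate reason for their rank would be helpful but changes no result.

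The interim argument does not stand. The stopping condition asks for a positive trend in mortality, not significance, so rank has no bearing on it. The review it governed also took place before version 3. Both interim analyses were assigned to an external independent statistician under the committee, and nothing in the documents suggests that the sponsor saw unblinded results before the change.

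The power figures do not rescue the point either. They measure the order, which is a defensible choice and is not being contested. The largest loss also needs HR 0.85 to apply to non-CV deaths, whereas the plan assumes 0.85 only for the primary composite.

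**Conclusion.** No change to the plan is needed. The test order, the gate and its consequence for all-cause mortality are fixed without ambiguity by SAP 3.1.3.2.1 and 3.4.4.3, and the older protocol lists are the earlier state of a logged change. Two editorial slips remain: SAP 1.2.2 still names five endpoints, and the version 3 log row gives a cross-reference where it could have given ranks. Neither affects an analysis, a decision or a claim.

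The order does lower the chance of a formal mortality claim, by about 0.04 to 0.09 when non-CV deaths are unaffected and by about 0.25 to 0.29 under a uniform effect. These sizes rest on assumed death counts and hazard ratios and do not condition on the earlier gates. They describe a legitimate trade-off with the CHD-death and CV-death claims, made at no cost in type I error. The conclusion assumes, as the documents indicate, that version 3 was fixed before the treatment code was broken.
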